10.1 Data Management

Prudent steps will be taken to ensure that all information will be kept confidential and secure, including medical and survey data. All survey data will be collected on-site by trial research nurse/staff and entered into REDCap (Research Electronic Data Capture), hosted at the University of Pennsylvania. We will implement multiple, redundant protective measures to guarantee the security of participant data. All data for this project will be stored on UPHS secure/firewalled servers. These data servers are maintained in a guarded facility behind several locked doors, with very limited physical access rights. They are also cyber-protected by extensive firewalls and multiple layers of security comparable to what is used in commercial financial transactions. This multi-layer system of data security, identical to the system protecting the University of Pennsylvania Health Systems medical records, greatly minimizes privacy risks. Direct identifiers for patients and their surrogates will be omitted from all analytic files.

10.2 Subject Confidentiality

Only authorized project personnel will have access to the data. All study data will be stored behind firewalls on UPHS servers; none will be stored on stand-alone PCs or laptops. All study personnel who work with these data will have undergone required human subjects training. We will implement multiple, redundant protective measures to guarantee the privacy and security of the participant data. All data for this project will be stored on the secure/ firewalled servers of the UPHS in data files that will be protected by multiple password layers. These data servers are maintained in a guarded facility behind several locked doors, with very limited physical access rights. They are also cyber-protected by extensive firewalls and multiple layers of communication encryption. Electronic access rights are carefully controlled by Penn system managers.

10.3 Subject Privacy

We will approach surrogates in the patient's room. We will offer them the option to speak in the patient's room or in an alternative private location. Individual-level medical data for patients will be kept confidential and will only be stored on highly secure servers available for patient-level data. Only authorized project personnel will have access to the data and the data will be stored on servers only and not stand-alone PCs or laptops. All study personnel who work with this medical data will have undergone all of the required human subjects training.

11. Human Subjects Protection

11.1 Potential Risks

Potential risks include loss of confidentiality, disappointment in not being able to participate in the described simulated trial and negative impact on clinician-family trust with the use of deception. We protect the data in several ways as outline in the data protection section. We purposefully selected a simulated trial of prioritizing decreases in FiO2 vs PEEP in weaning of mechanical ventilation as a trial that would unlikely result in excessive optimism and therefor would yield minimal disappointment once it is disclosed that it is a simulated trial.

11.2 Potential Benefits

Participants will be instructed that this is research, and like all research, it is being conducted with the primary goal of producing generalizable knowledge. Thus, the primary benefits to be gained are those related to the knowledge to be gained. However, patients, as well as their families, may benefit directly from the opportunities to discuss their thoughts on research participation. In addition, the knowledge to be gained in this study may help develop a simple way to increase research participation.

11.3 Risk/Benefit Assessment

Participants will be offered enrollment in a sham randomized controlled trial comparing the effects of prioritizing decreases in FiO2 vs PEEP in weaning of mechanical ventilation. Thus, temporarily deceiving patients on the purpose of the study. Importantly, the risk is minimal because: (1) their participation in the main study and decision whether or not to participate in the sham RCT will not affect the treatment their loved one receives; (2) the proposed intervention in the sham RCT is within standard of care for mechanically ventilated patients and is minimally invasive, so discussion about this sham RCT and intervention is not expected to lead to additional distress for the participant; (3) the evidence to date suggests that the behavioral nudges employed in this study are without ethical concerns (4) we offer participants the opportunity to opt-out after a thorough debriefing procedure. Difficulty recruiting patients is a widely recognized barrier to successful completion of clinical trials and a significant contributor to the cost of conducting such studies. If a simple intervention such as the behavioral economic nudges we are testing are found to increase trial recruitment without blunting perception of risk it could have a dramatic effect on future critical care trials.

12. Study Instruments

12.1 Pre-consent Nudge Survey

Family Attitudes towards Participation in Advanced Illness Research Survey

This is a survey to help us understand the relationship between patient's behaviors and their family's feelings about participation in medical research. Answering these questions is voluntary. The care of your loved one will not be impacted by whether or not you participate. Responses will be anonymous and confidential.

	Yes	No
My loved one would give directions to someone they didn't know:	0	0
My loved one would delay an elevator and hold the door for someone they didn't know:	0	0
My loved one would give clothes or goods to a charity:	0	0
My loved one would give money to a charity:	0	0
My loved one would offer to help a handicapped or elderly person across the street:	0	0
Many treatments used today that improve survival for patients in the intensive discovered through many patients' participation in research studies.	e care unit we	ere No
My loved one would participate in a research study if it was low risk to them	1.00	1.10
and the information learned may help other patients in the future.		

12.3 Risk Perception Assessment

Risk Assessment

1. On a scale of 1 to 7, how risky do you believe this study would be for participants?

Not Risky At All						Very Risky	
1	2	3	4	5	6	7	

2. Does the study seem...

	Yes	No
More risky than talking on the cell phone while driving?	0	0
More risky than receiving the flu vaccine?	0	0
More risky than flying on a plane?	0	0
More risky than driving 15 mph over the speed limit?	0	0
More risky than taking 3 times the recommended dose of a pain killer?	0	0
More risky than receiving stitches?	0	0
More risky than riding a motor cycle with no helmet?	0	0
More risky than getting a body piercing?	0	0
More risky than bungee jumping?	0	0

12.4 Surrogate Demographic Survey

□ Separated

Penn Medicine	Study ID
Demographic and Clinical information:	
Please answer the following to the best of your ability about yourself (all will be kept confidential and secure and will not be shared):	
1. Are you officially designated as the patient's durable power of attorney for health care? ☐ Yes ☐ No	8. Please specify your ethnicity: Hispanic or Latino Not Hispanic or Latino
2. Have you ever had a life-threatening illness or injury for which you needed life support to keep yourself alive? This type of care would usually mean that you were in an ICU, and being treated with a breathing machine or other machines or medicines necessary to keep you alive.	9. Please specify your race: American Indian or Alaskan Native Asian Native Hawaiian or Other Pacific Islander Black or African-American White or Caucasian Other
Yes □ No 3. Have you ever participated in a medical research trial? This would usually mean being asked for consent before taking an experimental medication or other intervention and being monitored for a response. Yes □ No	10. What is your highest level of completed education? Less than High School High School/GED Some College College Degree Post-College Degree (MA, Professional
4. Has anyone you known ever participated in a medical research trial? This would usually mean being asked for consent before taking an experimental medication or other intervention and being monitored for a response.	degree, PhD) 11. What is your relationship to the patient? □ Spouse
☐ Yes ☐ No 5. What is your gender? ☐ Male ☐ Female	☐ Adult child ☐ Parent ☐ Sibling ☐ Other blood relative ☐ Friend
6. What is your age? 7. What is the your marital status?	□ Other
☐ Widowed ☐ Married/Partnered ☐ Never married ☐ Divorced	

12.5 Patient Demographic Survey

Penn Medicine	Study ID
Please answer the following to the best of your ability about your loved one (all will be kept confidential and secure and will not be shared):	
1. In the past 3 months, approximately how long has the patient spent in a hospital or other health care facility?	5. What is the patient's gender?
☐ Less than 1 week	□ Male
☐ 1 week to 1 month	☐ Female
□ 1 month to 3 months	_
☐_Entire 3 month	6. What is the patient's age?
	7. What is the patient's marital status?
2. Before the patient's current Intensive Care (ICU) stay, have they ever had a life-threatening illness or injury for which they needed life support to keep them alive? This type of care would usually mean that they were in an ICU, and being treated with a breathing machine or other machines or medicines	 Widowed Married/Partnered Never married Divorced Separated
necessary to keep them alive.	8. Please specify the patient's ethnicity:
☐ Yes ☐ No ☐ I don't know 3. Has the patient ever participated in a medical	☐ Hispanic or Latino ☐ Not Hispanic or Latino
research trial? This would usually mean being asked	9. Please specify the patient's race:
for consent before taking an experimental	☐ American Indian or Alaskan Native
medication or other intervention and being	☐ Asian
monitored for a response.	 Native Hawaiian or Other Pacific Islander
☐ Yes ☐ No ☐ I don't know	☐ Black or African-American
4. Based on the information that has been shared	 □ White or Caucasian □ Other
with you about your loved one's condition, do you	
feel that he or she is:	10. What is the highest level of education the patient has completed?
□ Stable	□ Less than High School
 Improving Worsening 	☐ High School/GED
- And Sering	 ☐ Some College ☐ College Degree
	☐ Post-College Degree (MA, Professional

degree, PhD)

13. References

- 2. Ellenberg SS. Randomization designs in comparative clinical trials. The New England journal of medicine 1984;310:1404-8.
- 4. Altman DG. Statistics and ethics in medical research: III How large a sample? British medical journal 1980;281:1336-8.

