3.3 Secondary Outcome Variable(s)

Secondary outcomes included undue inducement, unjust inducement, patient and surrogate characteristics associated with enrollment. Undue inducement was defined as an interaction between intervention and risk perception on enrollment rate. Unjust inducement was defined as an interaction between intervention and highest level of education completed on enrollment rate.

4. Design

This is a single-blinded randomized controlled among surrogates of patients requiring mechanical ventilation admitted to one of ten ICUs across two University of Pennsylvania Health System (UPHS) hospitals.

5. Recruitment

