5.3 Accrual

We have received approval from the University of Pennsylvania IRB-approved protocol and obtained approval to conduct this study in all 6 ICUs located at the Hospital of the University of Pennsylvania and all 4 ICUs located at Presbyterian Hospital. Using an estimated baseline enrollment rate of 30% in the control group, a total of 182 participants achieves at least 80% power to detect a 20% absolute difference at alpha of 0.05. We will consecutively recruit all eligible surrogates from the ICU until we reach our target sample size. We will attempt visit each ICU session at least once a day. The research coordinator will approach eligible surrogates while they are present in the patient's room. For surrogates who initially defer a decision we will attempt to reengage the following day and each subsequent recruiting day until we either have a definitive decision or until the patient is ineligible. We anticipate that we can recruit at least 4 patients per week.

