6.2 Assignment

Group allocation will be determined by the REDCap randomization module with assignment probabilities of 50% to each group stratified by research coordinator.

7. Procedures

Study procedures are as following:

- 1. The research coordinator will review the electronic medical record of patients admitted to each of 10 ICUs to determine eligibility and documenting the results in the study screening database.
- 2. The research coordinator will contact the ICU attending of patients screened as eligible to confirm eligibility.
- 3. The research coordinator will visit each eligible patient's room to assess for the presence of visitors.
- 4. If visitors are present the research coordinator will enter patient information into the REDCap study module on the screening tablet.
- 5. The research coordinator will enter the room, identify themselves and confirm that the visitor is the patient's surrogate decision maker.
- 6. The research coordinator will ask the patient's identified surrogate decision maker if they are willing to hear about a research study.
- 7. Surrogate decision makers who indicate their wiliness to hear about a research study will then be randomized in the REDCap randomization module (as above).
- 8. If the participant is randomized to the intervention arm the research coordinator will follow the script (see below) introducing the survey. Following completion of the survey the research coordinator will then ask if they are willing to hear about a research trial.
- 9. If the participant is randomized to the control arm the research coordinator will follow the script (see below) introducing the sham mechanical ventilation weaning trial.

- 10. After the surrogate makes an enrollment decision (regardless of the decision) for the sham mechanical ventilation trial they will be asked to complete the risk perception assessment and demographic surveys.
- 11. If the surrogate askes for more time to make an enrollment decision the research coordinator will ask for a good time to return for a decision. Risk perception assessment and demographic survey data will be deferred until after a decision is made. The research coordinator will follow up the following day (or time set by surrogate) to seek an enrollment decision. Repeated attempts to obtain an enrollment decision will continue each recruitment day until a decision is made or until eligibility criteria is no longer met.

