- 12. Immediately following the sham trial enrollment decision, risk assessment and demographic surveys the research coordinator will debrief the surrogate (see script below).
- 13. The research coordinator will update the screening database with the results of the recruitment attempt.
- 14. The research coordinator will document additional clinical data from the electronic medical record for participating patients into the REDCap study database.
- 15. We will continue subject recruitment until target enrollment is reached.

8. Consent

A waiver of informed consent has been approved by the University of Pennsylvania Institutional Review Board. Once patients have been chart screened for eligibility, study personnel will approach potentially eligible surrogate. Study personnel will introduce themselves to the patient, inform the patient that they are part of a group conducting a research study, and ask permission to sit down and tell the patient more. Following the study procedures and debriefing the participant will retain the debriefing handout which includes instructions on how to withdrawal from the study.

9. Analysis Plan

As we do not have any strong a priori evidence that any of the collected demographic will be strongly associated with the primary outcome, we will perform an unadjusted analysis as the primary analysis. The primary outcome will be an intention-to-treat analysis of the proportion of participants who enroll in the sham clinical trial. The intervention arm will be compared to the control arm using a chi-square test. In secondary analyses, we will test for undue inducement by assessing the interaction between the study group and risk perception on enrollment rate. We will test for unjust inducement by assessing the interaction between study group and level of education on enrollment rate. Stata v14 will be used for all analyses. Unless otherwise specified, a p-value <0.05 will be considered significant.

We will conduct a post-hoc exploratory analysis of patient and surrogate variables associated with sham trial enrollment. We will have a third party with critical care trial recruitment expertise, blinded to the data, review and rank the variables based on their mechanistic plausibility to impact enrollment decisions. The number of included variables in the final model will be determined by the number of events (enrollments into the sham trial) to not exceed a 1:10 covariate to event ratio.

10. Confidentiality of Subjects and Data

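### Two questions on past trial participation have no look-back limit and are asked after the sham enrollment decision and before debriefing, so the outcome can leak into a candidate predictor of enrollment

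*Combined protocol and SAP*

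**What the plan says.** **Order of events.** In section 7, step 10, once surrogates have decided, whichever way, "they will be asked to complete the risk perception assessment and demographic surveys". Step 11 holds the surveys back until a decision exists. Step 12 puts debriefing last: "Immediately following the sham trial enrollment decision, risk assessment and demographic surveys the research coordinator will debrief the surrogate". Section 6.1 gives the same order.

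**The items.** Section 12.5 item 3 asks "Has the patient ever participated in a medical" research trial. Section 12.4 item 4 asks "Has anyone you known ever participated in a medical research trial". Neither is limited in time. Both carry a gloss saying what participation would usually mean: consent is sought, an experimental drug or other intervention follows, and the response is monitored. By contrast, 12.5 item 2, on earlier life support, is explicitly limited to the time before the current ICU stay.

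**The use.** Section 3.3 lists "patient and surrogate characteristics associated with enrollment" among the secondary outcomes. Section 9 studies them in a post-hoc exploratory model. A third party blinded to the data ranks the variables by plausibility, with at most one covariate per ten enrollments. No rule keeps the two participation items out.

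**The concern.** A surrogate who has just agreed believes, when filling in the forms, that the patient has joined a real ventilator trial. That surrogate has a reason to answer Yes to both items that exists only because of the enrollment decision. The patient is also someone the surrogate knows, which is why item 4 of the surrogate form is exposed. A surrogate who declined has no enrollment to count. Any resulting error would differ by outcome, and it would run in the direction that makes past research experience look like a predictor of enrollment.

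Past experience is a plausible candidate for the model, and a ranking made on plausibility, blind to the data, cannot detect contamination. Both items would be contaminated by the same event, so they could appear to confirm each other. Once the forms are completed, a Yes that counts the sham trial cannot be told apart from a Yes about earlier research.

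**Working it through.** **1. The plan's own figure.** Section 5.3 uses an "estimated baseline enrollment rate of 30% in the control group" and states that "a total of 182 participants achieves at least 80% power to detect a 20% absolute difference at alpha of 0.05". Section 6.2 gives "assignment probabilities of 50% to each group stratified by research coordinator". Taking the difference as an increase and the test as two-sided (neither is stated), with unpooled variance:

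n per arm = (1.960 + 0.842)² × (0.30×0.70 + 0.50×0.50) / 0.20² = 90.3, so 91 per arm and 182 in total.

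Power at 91 per arm is 80.3%. The stated 182 is reproduced. (The pooled-variance formula gives 93 per arm, or 186.)

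**2. Enrollers and decliners under the plan's assumptions.** 91×0.30 + 91×0.50 = 72.8, about 73 enrollers and 109 decliners. The one-in-ten rule then allows 7 covariates. If the intervention has no effect, 182×0.30 = 54.6 enrollers allow 5.

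**3. Model of the leak.** Let p be the true prevalence of earlier participation, the same in both groups (no true association). Let m be the share of enrollers who would otherwise answer No but count the sham trial. Neither figure is in the documents; both are assumptions.

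- Yes rate in enrollers: p + (1 − p)m
- Yes rate in decliners: p
- Spurious odds ratio: the odds of the first divided by the odds of the second
- Chance of p<0.05: two-sided Wald test of the log odds ratio, SE = √[1/(73·a(1−a)) + 1/(109·b(1−b))], where a and b are the two Yes rates

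Example with p = 0.15 and m = 0.10: a = 0.15 + 0.85×0.10 = 0.235. The odds ratio is (0.235/0.765)/(0.15/0.85) = 0.307/0.176 = 1.74. The log odds ratio is 0.554 with SE 0.385, so the chance of p<0.05 is about 30%.

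| p | m | Yes rate, enrollers | Spurious odds ratio | Chance of p<0.05 |
|---|---|---|---|---|
| 0.15 | 0 | 15.0% | 1.00 | 5% |
| 0.15 | 0.02 | 16.7% | 1.14 | 6% |
| 0.15 | 0.05 | 19.3% | 1.35 | 12% |
| 0.15 | 0.10 | 23.5% | 1.74 | 30% |
| 0.15 | 0.20 | 32.0% | 2.67 | 76% |
| 0.10 | 0.10 | 19.0% | 2.11 | 40% |
| 0.20 | 0.10 | 28.0% | 1.56 | 24% |
| 0.40 | 0.10 | 46.0% | 1.28 | 13% |

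A simulated chi-square test (20,000 runs) at m = 0.10 gives 40% for p = 0.10 and 25% for p = 0.20, in line with the table.

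**4. If decliners misread too.** With p = 0.15, 10% misreading in enrollers and 5% in decliners, the Yes rates are 23.5% and 19.3% (0.15 + 0.85×0.05 = 0.1925). The odds ratio falls to (0.235/0.765)/(0.1925/0.8075) = 1.29, and the chance of p<0.05 to about 11%.

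**5. With the items anchored.** If anchoring brings m to 0, the odds ratio is 1.0 and the simulated rejection rate is 4.5% to 5.0% for p between 0.05 and 0.20. The sample size stays at 182.

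**The case against.** The strongest reply is that the gloss printed with the items describes an intervention and monitoring as well as consent, and the stem is in the past tense. Shortly after a yes, nothing has been given and nothing monitored, so a literal reader would answer No. Patient item 3 also offers a don't-know option. This stands as a reason why misreading may be rare, even close to zero. It does not close the route: the gloss says only what participation would usually mean, and the consent step has just taken place.

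Decliners were also just asked for consent, so some of them might misread as well. That stands too, and step 4 of the working shows that it shrinks the effect. But only an enroller believes that the patient has actually entered a trial.

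The scope is narrow. The analysis is exploratory, has room for about 5 to 7 covariates, and may not select either item.

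The sham consent form, debriefing form and script listed in the contents are not in the text available for review. How coordinators introduce the surveys therefore cannot be checked, and no conclusion is drawn from that.

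**Conclusion.** The point holds as an open route for outcome-dependent error in two questionnaire items. The order of events and the missing time limit are plain in the documents. How often surrogates would count the sham trial is not. At an assumed 15% prevalence the spurious odds ratio runs from 1.0 (no misreading) to 2.67 (20% misreading). At 2% misreading the effect is negligible; at 10% the chance of a false positive is about 30%. These figures rest on assumed prevalence and misreading rates, no true association, no misreading by decliners, and the plan's 30% and 50% enrollment rates.

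A reader might infer three stronger things, none of which the documents support:

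- **That leakage does occur.** Nothing in the documents shows how surrogates read the items.
- **That all three participation questions are equally exposed.** Surrogate item 3 in section 12.4 asks about the surrogate's own participation, not the patient's, and is barely affected.
- **That the main results are at risk.** The primary chi-square test, the sample size and the undue and unjust inducement interactions (risk perception and education) do not use these items.

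The change is still worth making: the exposed analysis is a listed secondary outcome, and a contaminated answer cannot be identified later.

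**What to change.** Add a look-back limit to 12.5 item 3 and 12.4 item 4, in the way 12.5 item 2 already does. For the patient item: *Before the current hospital stay, has the patient ever taken part in a medical research trial?* For the surrogate item: *Before today, and not counting the study we have just discussed, has anyone you know ever taken part in one?* Surrogate item 3 may be anchored in the same way for consistency.

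Moving the items ahead of the decision is a poorer choice, because asking controls about research participation beforehand could itself act as a nudge.

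If data have already been collected with the present wording, leave the two items out of the exploratory model, or report them as possibly contaminated by the outcome.

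The cost is a few words on two forms and a minor IRB amendment, with no extra visits, staff or participants.
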